### ***CM and Cost Effectiveness***

One barrier to use of CM has been that the monetary costs of incentives can be prohibitive. Petry et al. (2000) developed and empirically tested a method for making CM more cost effective. It was an escalating variable-ratio schedule of reinforcement such that costlier rewards are provided less frequently. Using a lottery-based reward system, participants who continuously maintain drug abstinence earn the right to draw increasing numbers of tokens from a “fishbowl” containing hundreds of tokens. With this prize-based approach, the monetary value of incentives remains more modest, thereby increasing the potential for translation to “real life” clinical settings. Multiple studies have highlighted the potential of CM protocols that use variable-ratio reinforcement schedules as a cost-effective CM strategy (e.g., Petry et al., 2005b; Olmstead & Petry, 2009; Peirce et al., 2006).

### ***Remote Delivery of CM***

An effective CM intervention requires frequent and objective monitoring of the target behavior, which has traditionally been cumbersome on staff and patients and can limit the range over which health services can be delivered (Kurti et al., 2016). The use of technology in remotely monitoring behaviors and delivering incentives eliminates the practical barriers associated with in-person monitoring (Kurti et al., 2016; Dallery et al., 2019). This emerging CM intervention strategy has been used for studies targeting substance abuse (e.g., Alessi & Petry, 2013; Meredith et al., 2011; Oluwoye et al., 2020), weight loss (e.g., Unick et al., 2015), as well as medication adherence (Defulio et al., 2021a) and home-based health monitoring (Kurti et al., 2016). While they provide ample evidence that a mobile-based CM procedure can work in practice, all still require human involvement.

### ***DynamiCare Rewards App***

DynamiCare is an iOS and Android app that provides several highly innovative features that overcome barriers to CM adoption, including fully automating CM methodology (monitoring/incentivizing of target behavior and dispersal of rewards). In addition to Virginia Commonwealth University, this app is currently being used at multiple research universities, such as Johns Hopkins University, Massachusetts Institute of Technology, University of Chicago, Western Michigan University, and University of Vermont. DynamiCare Health, Inc. has been awarded several grants and prizes for the development and implementation of the DynamiCare Rewards app, including Small Business Innovation Research (SBIR) Phase I and Phase II grants from NIH – NIAAA. To date, use of this app has focused exclusively on SUDs.

Recent trials using the DynamiCare Rewards app have demonstrated its efficacy and utility in delivering CM. Kurti et al. (2020) conducted a pilot study of the DynamiCare Rewards

app targeting cigarette smoking in pregnant women. They demonstrated feasibility and found that those in the CM group had higher quit rates compared to controls (Kurti et al., 2020). DeFulio et al. (2021b) found CM delivered via the DynamiCare Rewards app significantly increased clinic appointment attendance and drug abstinence compared to matched controls among patients with Opioid Use Disorder. They also concluded that the DynamiCare Rewards app was usable, acceptable, and similarly effective to in-person CM (DeFulio et al., 2021b).

### ***Incentives for Self-Reporting of Prescription Opioid Use***

Finan et al. (2017) recently investigated the variability of Rx opioid use and associations with pain and related factors in patients with sickle cell disease who received incentives for completing a daily electronic diary ( $N=45$ ). They found that greater pain and pain catastrophizing were associated with greater use of short-acting opioids, and negative affect was associated with greater use of long-acting opioids. Adherence to self-monitoring was problematic in their study, with one-fourth (25%) of the sample excluded for having <25% of self-reports, with an additional 25% of the remaining sample having missing data. These findings highlight the value of remote self-monitoring of pain severity, related factors, and Rx opioid use for providing information that aids effective opioid prescribing. Results also demonstrate the need to better understand how to improve adherence to self-monitoring of these variables.

### **Summary**

Adherence is a problem in many fields of behavioral medicine and while CM has had the biggest impact, practical barriers have limited implementation in “real life” care. The present study sought to bridge the gap with an RCT of the DynamiCare Rewards app for promoting daily self-monitoring of pain severity, related factors, and Rx opioid and alcohol use in a sample of individuals with chronic pain. Comprehensive information on pain severity and medication use

has the potential to help physicians make better opioid prescribing decisions, addressing the opioid epidemic and improving public health.

## **Methods**

### **Participants**

Participants will be individuals seeking to participate in research studies through ResearchMatch.org. Individuals will be eligible to participate in the study if they meet the following criteria: 1) at least 18 years of age; 2) own a study-compatible smartphone (iPhone or Android device); 3) report non-cancer related chronic pain of at least 3 months' duration; 4) able to provide informed consent for study participation; 5) report having chronic pain as part of their ResearchMatch.org profile; and 6) prescribed  $\geq 1$  opioid medication(s) for pain management in their lifetime. Individuals will be excluded from study participation if they meet any of the following criteria: 1) currently pregnant; 2) presenting with language barriers, cognitive impairment, or serious medical or psychiatric illness that in the opinion of the Investigator would preclude them from providing informed consent or participating in the study; and 3) visual impairment or motor impairment that would interfere with use of a smartphone.

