## **Aims**

The specific aims of this Phase 1 therapy development project are to:

*Aim 1:* Compare number of completed daily self-monitoring surveys in CM and C groups. One hypothesis was tested:

*Hypothesis 1:* CM group participants will complete more daily self-monitoring surveys compared to control group participants.

*Aim 2:* Compare longest sustained period of daily survey completion in CM and C groups. One hypothesis was tested:

*Hypothesis 1:* CM group participants will have a longer sustained period of daily survey completion compared to control group participants.

*Aim 3:* Examine agreement between daily survey and follow-up visit reports of alcohol and Rx opioid use in CM and C groups.

*Aim 4:* Examine feasibility and acceptability of CM app implementation targeting self-monitoring of pain severity, related factors, and use of Rx opioids and alcohol.

*Aim 5:* Estimate effect-size to be used to perform power analyses and sample size calculations as part of the design of a larger RCT.

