### ***Baseline Assessment***

Following informed consent, participants will complete a series of computer-administered questions via REDCap (demographic information; medical and mental health history; The Brief Pain Inventory; Pain Self-Efficacy Questionnaire; Pain Catastrophizing Scale; Hospital Anxiety and Depression Scale; Pittsburgh Sleep Quality Index; and 28-day Timeline Followback). Baseline assessment will take approximately 30-45 minutes to complete. If participants do not complete the baseline survey within two days of completing the screener, they will be sent a reminder email to complete the survey. If participants do not complete the baseline survey within three days post screening, they will be called. At the end of their baseline survey, participants will be asked their preference for a 5-10-minute telephone or Zoom call to finish their baseline visit. They will then be informed that within the next business day they would receive a call or email from study staff to set up their Zoom or phone appointment to complete the baseline visit. Participants will be called daily for one week following baseline survey completion until they are reached to complete the baseline call. Participants who can not be reached by telephone or Zoom within one week of completing the baseline survey will not be enrolled or randomized into the study.

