***Follow-Up Survey Only***

**TLFB (Sobell & Sobell, 1992).** The TLFB is a widely-used, semi-structured interview that uses a calendar to retrospectively collect daily information about substance use. It has been shown to have good reliability and validity and is widely considered the “gold standard” of quantity and frequency substance use assessment. To accommodate the remote study procedures, the TLFB was adapted from interviewer to computer administered (via REDCap), which has been found to be reliable and valid (e.g., Martin-Willett et al., 2020). The TLFB was used to obtain detailed past 28-days frequency of opioid pain medication and alcohol use information.

**Acceptability.** Participants were asked to answer questions about satisfaction, acceptability, and feasibility on a 0-10 scale based on those used in a previous RCT investigating an app developed for chronic pain patients (Jamison et al., 2017).

**Validity and Accuracy of Responses.** All participants were asked how honest they were in completing the daily survey (response options: I was very honest, I was honest most of the time, I was honest some of the time, I was honest once in a while, I was not honest at all). CM participants were additionally asked how much the rewards made a difference in how accurately

they reported information in the daily survey (response options: Not at all, very little, little, somewhat, much, to a great extent, completely).

**Self-Report of Impact of Behavioral Incentives to Adherence.** CM participants were asked how much the rewards made a difference in whether they completed the daily survey (response options: Not at all, very little, little, somewhat, much, to a great extent, completely).

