### ***Outcome Measures***

As shown in Table 4, the primary outcome measures are the number of completed daily self-monitoring surveys and the longest period of sustained adherence to survey completion. It is hypothesized that those in the CM group will complete more daily self-monitoring surveys and have a longer sustained period of daily survey completion compared to controls. The number of completed daily surveys and duration of continuous daily survey completion will be compared between CM and Co groups using independent *t*-tests.

Secondarily, descriptive statistics will be used to summarize CM participants' self-report of the impact of behavioral incentives on adherence. Mean time to complete the daily surveys between CM and Co groups will be compared using an independent *t*-test. Pain experience and

related variables from baseline will be compared to follow up responses for the total sample using paired *t*-tests. The daily survey item responses will be summarized for the overall sample using descriptive statistics. Associations between daily survey and follow-up TFLB for alcohol and prescription opioid use data for the overall sample and each study group will be examined using Spearman's correlations. Descriptive statistics will be used to summarize self-report validity and accuracy of responses. Feasibility and acceptability of CM app implementation will be examined by comparing follow-up acceptability survey ratings for each group using independent *t*-tests.

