**Table 4**

*Outcome Measures Overview*

Name	Time Frame	Brief Description
Number of daily surveys completed	28-day daily survey period	This primary outcome is consistent with previous CM studies.
Longest period of sustained adherence to daily survey completion	28-day daily survey period	Largest number of consecutive days wherein daily surveys were completed. This primary outcome is consistent with previous CM studies.
Mean frequency of alcohol and prescription opioid use (days of use)	28-day daily survey period to follow up	Spearman's correlations between daily survey and TLFB data for alcohol and prescription opioid frequency (days of use) were conducted for the entire sample, the CM group, and the Co group.
Mean time to complete the daily surveys	28-day daily survey period	Daily survey completion time (the amount of time from daily survey start to finish).

Name	Time Frame	Brief Description
Mean CM app feasibility and acceptability survey ratings	Follow up	CM app satisfaction, acceptability, and feasibility survey ratings (on a 0-10 scale; administered at follow-up) based on those used in a previous RCT investigating an app developed for chronic pain patients (Jamison et al., 2017).
Self-report validity and accuracy of responses	Follow up	Ratings of how honest participants were in completing the daily survey and how much the rewards made a difference in how accurately CM participants reported information in the daily survey.

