**Medical and Mental Health History [Baseline Visit Only]**

1. How many days have you experienced medical problems in the past 30 days? (response 0-30)
2. Check all of the following medical conditions that a doctor, nurse, or other health professional has told you that you have.
  - a. Heart disease (e.g., angina, heart attack, or congestive heart failure)
  - b. High blood pressure
  - c. High cholesterol
  - d. Migraines
  - e. Diabetes
3. As before, check all of the following medical conditions that a doctor, nurse, or other health professional has told you that you have.
  - a. Hepatitis
  - b. Liver disease
  - c. Pancreatitis
  - d. Asthma
  - e. Chronic obstructive pulmonary disease (COPD) (e.g., emphysema or bronchitis)
  - f. Arthritis
  - g. Other (free response)
4. Check all of the following mental health conditions that a doctor, psychologist, or other health professional has told you that you have.
  - a. Depression
  - b. Anxiety
  - c. Bipolar Disorder
  - d. Attention-Deficit/Hyperactivity Disorder
  - e. Substance Use Disorder
  - f. Other (free response)
5. Are you currently prescribed any opioid medications (such as OxyContin, Vicodin, Tylenol 3, Percocet, or morphine)? (yes or no)

6. Are you currently prescribed any other types of pain medications (such as *Gabapentin* or *Pregabalin*)? (yes or no)
7. Are you currently prescribed any benzodiazepine medications (such as Xanax, Ativan, Valium, or Klonopin)? (yes or no)

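### The Aim 3 opioid correlation is run over the whole sample and whole arms, so participants with no opioid use inflate it by an amount the plan neither limits nor reports

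*Combined protocol and SAP*

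**What the plan says.** - **Eligibility** (Methods, Participants, criterion 6): one or more prescribed "opioid medication(s) for pain management in their lifetime". Neither current opioid use nor a current prescription is required, and there is no alcohol criterion.
- **Aim 3** (Aims): "Examine agreement between daily survey and follow-up visit reports of alcohol and Rx opioid use in CM and C groups". No hypothesis is attached.
- **Analysis** (Data Analysis Plan, Outcome Measures): daily-survey and follow-up "alcohol and prescription opioid use data for the overall sample and each study group will be examined using Spearman's correlations". Table 4 gives the variable as days of use: "correlations between daily survey and TLFB data for alcohol and prescription opioid frequency (days of use) were conducted for the entire sample", and for each group.
- **Sources**: for the follow-up Timeline Followback (TLFB), "The TLFB was used to obtain detailed past 28-days frequency of opioid pain medication and alcohol use information". Appendix A, items 8 and 9, asks each day about the previous day's prescription medications, with opioids as one option.
- **Current prescription**: Appendix B, Medical and Mental Health History, item 5, is a yes/no baseline question on whether the participant is currently prescribed an opioid. It is not used to define any Aim 3 analysis set.

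No section restricts the correlation to people who use or are prescribed opioids, stratifies it, or adds a second measure of agreement.

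**The concern.** A participant who takes no opioid during the 28 days will usually record 0 days in the survey and 0 days in the TLFB. Such pairs carry little information on how well a user's two reports match. In a rank correlation they form one tied block at the bottom, clearly separated from most users, and that separation alone produces a positive coefficient. The result then answers largely whether a person uses opioids at all.

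The accuracy of opioid reporting is central to the project's stated purpose, and the pilot is meant to supply benchmark data. A coefficient that looks like good agreement could be carried forward when users' own reports match less well. Changing the statistic alone would not cure this: a paired difference over the whole sample would be diluted by the same zeros.

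**Working it through.** The plan states no expected correlation, agreement target or share of current users, so there is no figure of its own to reproduce here. The sizing text serves the primary *t*-tests and does not bear on this point.

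**Inputs.** From the documents: days of use over 28 days; 80% retention (Sample Size Justification); 46 CM and 35 Co participants (Randomization). Assumed, because the documents are silent: the share *z* of zero-zero pairs, the correlation *r* between users' two reports, and survey completion.

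**Formula.** Put ranks on a 0 to 1 scale.
- Non-users sit at *z*/2 and users average *z* + (1 − *z*)/2, so the two blocks are 1/2 apart. The between-block variance is *z*(1 − *z*)/4.
- Users' ranks spread over a width of 1 − *z*. They contribute a within-block variance of (1 − *z*)³/12.
- If every user has at least one day in both sources, the whole-sample coefficient is

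  rho = [3*z* + *r*(1 − *z*)²] / [3*z* + (1 − *z*)²].

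With *r* = 0 this is 3*z*/(1 + *z* + *z*²).

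| Zero-zero share *z* | rho if *r* = 0 | rho if *r* = 0.8 |
|---|---|---|
| 10% | 0.27 | – |
| 25% | 0.57 | 0.91 |
| 40% | 0.77 | 0.95 |
| 50% | 0.86 | 0.97 |
| 60% | 0.92 | 0.98 |

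Example at *z* = 0.6, *r* = 0: 1.8/(1 + 0.6 + 0.36) = 1.8/1.96 = 0.92.

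**Threshold for 0.9 with *r* = 0.** Solve 0.9*z*² − 2.1*z* + 0.9 = 0: *z* = (2.1 − √1.17)/1.8 = 0.566, about 57%.

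**Simulation at the expected follow-up size** (80 × 0.8 = 64), with users' days uniform on 1 to 28 and unrelated: mean 0.57 (95% range 0.45 to 0.69) at 25% zero-zero pairs; 0.86 (0.81 to 0.91) at 50%; 0.92 (0.88 to 0.95) at 60%.

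**Missed surveys.** A user who skips surveys can score 0 in the survey and more than 0 in the TLFB, which blurs the separation. Here a missed survey is taken to contribute no use day, and completion varies between people (Beta distribution with precision 1.5, an assumption). Users' reports are again unrelated:

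| Mean completion | rho at *z* = 40% | rho at *z* = 60% |
|---|---|---|
| 70% | 0.74 | 0.89 |
| 50% | 0.68 | 0.83 |
| 30% | 0.57 | 0.71 |

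If everyone completed exactly 70%, the value at *z* = 60% would be about 0.91, so the reduction depends on how unevenly surveys are missed. The users-only correlation is 0 in all these settings.

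**Size of a restricted set.** Co: 35 × 0.8 = 28. If 30% to 60% are current users, that is 8.4 to 16.8, or about 8 to 17 people. With unrelated reports, the coefficient would by chance fall within about ±0.71 for 8 people and ±0.49 for 17.

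**Selecting on any use day in either source.** For two independent sparse counts with means of 0.5 to 1 day, the full-set correlation is 0. Dropping only the zero-zero pairs gives about −0.2 to −0.6. That selection manufactures disagreement.

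**The case against.** The strongest reply has five parts.

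1. *The non-user share is unknown.* This stands. At 10% zero-zero pairs the worst-case coefficient is only 0.27. A reader might infer that the trial would report near-perfect agreement, above 0.9, from unrelated reports. The documents do not support that: it needs more than about 57% zero-zero pairs and nearly complete or evenly completed surveys.
2. *Wholly unrelated reports are an extreme case.* This also stands. They come from the same person over the same 28 days, and at a users' correlation of 0.8 the inflation is modest.
3. *Zero-zero pairs are not empty of information.* This stands in part. Someone without a prescription may still take opioids: Appendix A, item 10, includes medication not prescribed for the participant, and Table 1 counts this as misuse. Consistent denial is part of agreement. A reader might also infer that baseline item 5 already records use; it records prescription.
4. *Aim 3 is secondary, has no hypothesis, and sits in a Stage I pilot.* True, and it limits the weight of the point. It does not make the coefficient easier to interpret.
5. *Other planned summaries would reveal low use.* Only partly. Daily responses are summarised for the overall sample, but no count of zero-zero pairs is planned.

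A reader might further infer that the CM and Co coefficients will differ because their non-user shares differ. That is possible, but no comparison of the two coefficients is planned and nothing in the documents shows unequal shares.

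**Conclusion.** The point holds in a limited form. As planned, the opioid coefficient mixes whether people use with how well users' reports match, and the plan gives no means of separating the two. In the worst case the zero-zero pairs alone yield about 0.57 to 0.92 for shares of 25% to 60%. With person-varying completion averaging 30% to 70%, the 60% figure falls to about 0.71 to 0.89. With users' reports correlated at 0.8, the coefficient moves only to 0.91 to 0.95 at shares of 25% to 40%.

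The non-user share, the completion pattern and the users' correlation are assumptions, not figures from the documents. The structural facts are in the text: lifetime eligibility, a whole-sample and whole-arm correlation, and an unused baseline prescription item. The lifetime criterion is not itself an error; the problem lies in the choice of analysis set.

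**What to change.** Amend the Outcome Measures section and leave eligibility unchanged.

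1. Keep the planned whole-sample and per-arm Spearman coefficients, but state that for opioids they largely reflect use versus no use.
2. Add, as the main opioid agreement result, the same analysis in participants currently prescribed an opioid at baseline (Appendix B, item 5). Give the number of participants and a confidence interval for each arm.
3. Report per arm, for opioids and for alcohol, the count and percentage of pairs that are zero in both sources and of pairs that are zero in one source only.
4. Do not define the analysis set by any use day in either source, because this selects on the outcome and biases the correlation downward.

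The cost is wording and a short table; the data are already to be collected. The restricted set will be small (about 8 to 17 Co participants if 30% to 60% are current users) and its interval wide. It also leaves out non-prescribed use, which the whole-sample table in step 3 still shows. Whether the TLFB is given at baseline, on which Baseline Assessment and Table 3 differ, is a separate point and this change does not depend on it.

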### **Study Procedures**

#### ***Recruitment***

Participants will be recruited through ResearchMatch.Org. ResearchMatch.Org is an online platform that allows researchers to recruit from a pool of people who have signed up to receive emails about potential research study participation opportunities. A recruitment email will be distributed one to two times per week to 20 to 400 unique ResearchMatch.org participants each time from this potential research participation pool who listed chronic pain conditions as part of their ResearchMatch.org profile. The recruitment email will include a

description of the study and a link to the REDCap screening survey imbedded in a button labeled "Yes, I'm interested."

